1 PROTOCOL SUMMARY

1.1 SYNOPSIS

Title:	Use of Behavioral Economics in Repeat SARS-CoV-2 Antibody Testing in Disadvantaged Communities
Grant Number:	3R33AG057395-04S1
Study Description:	Uptake of SARS-CoV-2 testing in underserved populations is subject to barriers related to resources and behaviors that may differ within communities and even households. Testing for SARS-CoV-2 antibodies in underserved populations can play an important strategic role. It is important to understand barriers and actionable facilitators of testing in underserved populations to address those most in need.
Objectives* :	Primary Objective: This project aims to evaluate the effectiveness of risk-based messaging and incentives that promote repeated testing for SARS-CoV-2 antibodies. Secondary Objectives: To understand social and behavioral determinants of COVID-19 testing and variations within sub-groups of this population.
Endpoints* :	Primary Endpoint: Characterize barriers to access, bias, risk attitude and incentive preferences through outreach and survey responses. Secondary Endpoints: Identify groups that may partition facilitators to testing into minimal and maximal effectiveness. Evaluate interventions and their heterogeneous treatment effects on social determinants and address barriers to test participation in a randomized trial.
Study Population:	2,160 individuals (540 families) from the largest Federally Qualified Health Center (AltaMed Health) in Los Angeles, California.
Phase* or Stage:	Stage III clinical trial
Description of Sites/Facilities Enrolling Participants:	AltaMed Health Services is one of the largest qualified health centers in the United States. The Commerce clinic site will be a participating site enrolling participants. The study does not intend to include sites outside of the United States.
Description of Study Intervention/Experimental Manipulation:	Using a random sample of households, we will recruit participants to conduct a randomized 2 x 2 (Messaging x Incentive) factorial experiment, in which participants complete a comprehensive set of social and behavioral surveys to identify determinants of commitment to testing.
Study Duration* :	24 months
Participant Duration:	12 months

1.2 SCHEMA

1.3 SCHEDULE OF ACTIVITIES

Assessment	Screening: Baseline (Month -3 to Month 0)	Baseline, Enrollment, Randomization: (Day 1)	Intervention start: (Month 1)	Intervention end: (Month 6)	Follow-up period: (Month 7 to Month 12)
Patient-level Assessments					
Informed Consent Form		X			
Demographics			X		
Inclusion/Exclusion Criteria	X	X			
Social Determinants of Health Survey		X		X	
Visit-level assessments					
Antibody Testing			X	X	

Adverse Events			X	X	X
----------------	--	--	---	---	---

2 INTRODUCTION

2.1 STUDY RATIONALE

SARS-CoV-2 virus has created one of the most challenging public health emergencies in modern history and antibody testing could be an important tool for responding to this pandemic. Uptake of SARS-CoV-2 testing in underserved populations is subject to barriers related to resources and behaviors that may differ within communities and even households. Testing for SARS-CoV-2 antibodies in underserved populations can play an important strategic role for several reasons. First, antibody testing is critical for public health surveillance and planning as it can identify both active and recovered infections. This helps us identify the extent of exposure in the community and learn more about illness severity and the mortality rate. This is crucial information for policy makers as they plan pandemic response to reduce disease burden and disparities. Second, antibody testing is also an important clinical tool and providers can choose from several FDA approved antibody tests with high specificity and sensitivity.¹ Finally, although the science is still uncertain, antibody testing might be used as a tool for identifying populations that can safely return to work or for prioritizing scarce PPE resources. However, antibody testing to date in the US has been limited. It is important to understand barriers and actionable facilitators of testing in underserved populations to address those most in need. We need to understand how to increase uptake of testing among vulnerable populations and how to encourage testing and retesting in general. Messaging, financial incentives, social and personal factors as well as the effect of learning of your first test results have implications for controlling the spread of the virus. A negative test result might promote prevention behaviors for people who thought they were previously infected.²

Our study, which will enroll and track a representative cohort of 2,160 persons (540 family clusters) for SARS-CoV-2 antibodies and repeatedly test them for antibodies, is significant for several reasons. First, it will allow us to track the evolution of the pandemic in the largest federally qualified health center (FQHC) in the United States. Second, we will be able to observe how the risk of infection is evolving differently in low-income underserved populations as compared to the general population. Third, repeat antibody testing of those who were seropositive in the first wave of testing will allow us to test how well antibodies maintain their presence at a second test 6-months later. There is preliminary evidence that antibodies wane over time, however current evidence is limited to few studies and small sample sizes.³ Fourth, and most importantly for scalable, generalizable, findings, we will find actionable ways to motivate repeat testing and we will be able to tailor those ways to the social and behavioral characteristics of the persons being tested.

2.2 BACKGROUND

In a prior study,² we asked people on a 10-point scale how likely they were to have had COVID-19. About 20% of the sample reported 7 or higher on this 10-point scale, however only 4% of the sample tested positive. This suggests antibody testing has a large potential to correct beliefs about past infection and promote retesting for those who are antibody negative. However, a positive test could potentially reduce willingness to participate in repeat testing. Among those who tested positive, about 23% of the sample reported a 1 or 2 on a 10-point scale on how likely they were to have had COVID-19. These people may be less likely to retest for studies trying to depict the immune response over time. Underserved populations face different barriers to testing and these may vary within different communities and households. The diversity in Los Angeles allows us to assess how barriers to antibody testing differ for vulnerable groups. Data from our prior study show that Blacks and Latinos were 27 percentage points and 14 percentage points less likely to participate in testing compared to their white counterparts.² We also find that those with household income less than \$50,000 were 17 percentage points less likely to take-up antibody testing compared to those with household income greater than \$100,000. It is important to understand why these disparities exist. The proposed research will shed light on this issue by evaluating barriers/facilitators of testing including

beliefs about COVID-19, mistrust of healthcare, insurance, and cultural factors. More importantly, we will study the behavioral, social and cultural factors that make actionable facilitators minimally and maximally effective. Many individuals may react differently to antibody test results. Our preliminary analysis suggests that the reactions to test results vary across subgroups. For example, lower income families and minorities are more likely to test positive, but less likely to think they have already had COVID-19. This mismatch between beliefs and serostatus might imply lower motivation to receive testing. Similarly, a larger portion of Blacks and Latinos are low-income, and many cannot work from home. A positive antibody test could have a larger increase in economic activity for this population if their perceived risk of leaving the house for work is reduced. This study will allow for improved understanding of the factors contributing to uptake of COVID-19 testing in underserved populations, and enhance our understanding of public health and health behaviors.²

2.3 RISK/BENEFIT ASSESSMENT

2.3.1 KNOWN POTENTIAL RISKS

The potential risks associated with participation in this study include 1) disclosure of survey responses, 2) disclosure of test results and 3) small levels of discomfort from a needless blood draw. It is also possible that participants do not know how to interpret their results, which could cause anxiety or undue reductions in prevention behavior. The antibody test involves a skin prick on rare occasion lead to prolonged bleeding. People who take medicines called blood thinners may have some bleeding from the site for a short time after the test is over.

2.3.2 KNOWN POTENTIAL BENEFITS

All participants will receive free serology testing. Demand for testing is very high and tests are relatively expensive. In addition, accurate knowledge of serostatus is a benefit for participants. If participants increase preventative behavior in response to antibody testing then the research will also benefit others in society by reducing the spread of COVID-19.

Answering the research questions for this study is critical for designing effective and equitable COVID-19 testing programs. This study will help understand the barriers to serology testing, which will be important as serology increasingly used to inform policy. It will also help the world understand how people respond to learning their serology test results, which will help us better understand how best to use testing as a policy tool. Finally, it will provide important evidence on how antibodies wane after acute exposure, how long they remain in the system, and whether people can be re-infected. In sum, the risks of this study are small relative to the potential benefits in identifying active and recovered COVID-19 infections for public health planning.

2.3.3 ASSESSMENT OF POTENTIAL RISKS AND BENEFITS

We will take great measures to protect against the risks highlighted above.

1. Protections against disclosure risks: Disclosure of survey responses or test results is highly unlikely. The CLIA lab will only have participant study ID and specimen barcode; they will not have any patient identifying information. Data will be recorded with SSL protected web sites to a data warehouse, and transferred over secure network protocol. Data will be kept in a HIPAA compliant version of REDCap and in encrypted files on a secure research computing cloud at USC Schaeffer Center facilities.
2. Protections against risks associated with learning results: All participants will receive a debrief after each serology test to inform them of what their test results mean for them. Communication of test results will align with the Abbott assay Fact Sheet provided by the FDA. The results communication will also follow CDC guidelines which suggest that individuals should continue preventive behaviors irrespective of test results and those who are symptomatic should obtain PCR test to check for active infection. We will also

have a hot-line that participants can call if they have any questions about their results and what they mean.

Answering the research questions for this study is critical for designing effective and equitable COVID-19 testing programs. This study will help understand the barriers to serology testing, which will be important as serology increasingly used to inform policy. It will also help the world understand how people respond to learning their serology test results, which will help us better understand how best to use testing as a policy tool. Finally, it will provide important evidence on how antibodies wane after acute exposure, how long they remain in the system, and whether people can be re-infected. In sum, the risks of this study are small relative to the potential benefits in identifying active and recovered COVID-19 infections for public health planning.

3 OBJECTIVES AND ENDPOINTS

OBJECTIVES	ENDPOINTS	JUSTIFICATION FOR ENDPOINTS
Primary		
To evaluate the effectiveness of risk-based messaging and incentives that promote repeated testing for SARS-CoV-2 antibodies	Main effect of incentives, the main effect of messaging strategy, and the interactions between incentives and messaging and covariates; seropositive status	We have found that providing at-risk incentives that can be insured with repeat health behavior outperforms direct cash payments of the same expected value.
Secondary		
To understand social and behavioral determinants of COVID-19 testing and variations within sub-groups of this population.	Characterize barriers to access, bias, risk attitude and incentive preferences through outreach and survey responses. Identify groups that may partition facilitators to testing into minimal and maximal effectiveness.	covariates

4 STUDY DESIGN

[figure not shown]
4.1 OVERALL DESIGN

Social determinants need to be understood in the context of actionable facilitators (things COVID-19 policymakers can do) to encourage repeat testing. We will study two types of facilitators (messaging and financial incentives) and evaluate the heterogeneity of treatment response based on the characteristics of those tested. We will conduct a 2 x 2 (messaging x financial incentive) factorial design (Aim 3) that stratifies on social and behavioral determinants (Aim 2) collected as part of an initial survey (Aim 1). We have been studying ways to identify powerful incentives for repeated health behaviors. We have found that providing at-risk incentives that can be insured with repeat health behavior outperforms direct cash payments of the same expected value. Individuals were 70% more likely to return to a health screening when insuring against losing a baseline incentive than they were when paid cash ($p < 0.01$).⁴ In addition, in a recent study we showed that disadvantaged patients at a federally-qualified health center were more likely to repeat a health behavior twice each week over 12 weeks when repetition

was insuring against losing a weekly incentive than if they were paid equivalently in cash (see Figure 1; $p < 0.05$).

5

Figure 1. Insurance (loss protection) vs. cash (control) incentive for repeat health behavior among disadvantaged persons (N = 151)

2 x 2 Stratified Randomization

Messaging (Factor 1): We will develop simple messaging that frames the decision to test in terms of either: (i) family risk, or, (ii) personal risk. These methods will be piloted, but will be of the form "Antibody testing will help you understand your family's risk of getting COVID-19"; and, "Antibody testing will help you understand your risk of getting COVID-19". Family risk framing may engender concern for loved ones. It may also make it easier to mentally simulate family burdens with COVID-19 such as knowing how several people in the family becoming sick could adversely affect the lives of everyone in the family. We hypothesize that the family framing will result in greater uptake of testing and greater repeat testing.

Incentives (Factor 2): We have been studying incentives for repeat testing since 2015.⁴ We have found that low-income persons respond better to insuring at-risk rewards with repeat behavior than they do to cash payment.⁵ For example, suppose for your first test you are given as an incentive that offers an 80% chance of winning \$52. You then are told you can guarantee winning this lottery by having a second COVID-19 test in 8-months. This is preferable to a \$10 cash payment (i.e., the cost of the insurance against losing an 80:20 bet on \$52) in 8-months. To low-income persons, delivering an attractive lottery incentive for baseline testing and then letting persons insure this lottery with repeat testing may better encourage retesting by giving peace-of-mind and relieving them of worrisome distractions about money that they may already face. We will construct two incentives for this factor: (i) a baseline incentive offering a 90% chance of \$60; (ii) a repeat financial incentive. For (ii) Group 1 receives insurance on winning the baseline incentive; Group 2 receives a lottery incentive offering a 1 in 25 chance of winning \$150. The expected reward for both Group 1 and 2 for having completed both baseline and retest is \$60 (i.e., program costs are the same). In prior work, we've shown that insuring against losing a lottery was more effective than cash payments in the cost of insurance. Here we explore if this also holds true against low-probability and high-reward lotteries for which people may be optimistic about winning.

Messaging and incentives may interact. For example, thinking about the safety of your family after a family-framed message may make insuring against losing a lottery more attractive than another risky lottery.

Testing in a Diverse Population: Sampling low-income populations is important for research on disparities, however, recruiting this population is challenging because they often lack consistent contact information, do not have internet access, and mistrust research. We will use a novel way of recruiting this population by partnering

with AltaMed Health Services, the largest FQHC in the United States that serves overwhelmingly a low-income and minority population. Partnering with an FQHC will build trust and also provide us access to reliable contact information. In a pilot study, we were able to recruit over 50 families for antibody testing within just 2 days at a local FQHC. AltaMed Health Services is our partner on our parent grant R33 AG057395; we have worked with them for over 10 years. We will work with the AltaMed Patient Centered Research Advisory Committee (PC-RAC) which is committed to ensuring that all research conducted within or in collaboration with AltaMed addresses patient and community needs. This committee aims to create a research program that is responsive to patient priorities and concerns, emphasizes community-based participatory research principles, and assures research findings improve patient health through strategic program and policy recommendations to promote economic, social, and racial justice. The PC-RAC is administered through AltaMed's Health Equity and Access for Latinos (HEAL) project whose mission is to develop a patient/community engaged research process. We will recruit two patients who have tested positive for COVID-19 to supplement this existing group. The Community Advisory Board will meet quarterly for this project to inform the development of study materials and review findings.

4.2 SCIENTIFIC RATIONALE FOR STUDY DESIGN

Repeat testing for SARS-CoV-2 antibodies in disadvantaged communities will help identify active and recovered infections over time, and, as we learn about antibody protection, it may help identify persons who have immunity. Many questions about social barriers and behavioral facilitators remain unanswered.

4.3 JUSTIFICATION FOR INTERVENTION

Social determinants need to be understood in the context of actionable facilitators (things COVID-19 policymakers can do) to encourage repeat testing. We will study two types of facilitators (messaging and financial incentives) and evaluate the heterogeneity of treatment response based on the characteristics of those tested. We will conduct a 2 x 2 (messaging x financial incentive) factorial design (Aim 3) that stratifies on social and behavioral determinants (Aim 2) collected as part of an initial survey (Aim 1). We have been studying ways to identify powerful incentives for repeated health behaviors. We have found that providing at-risk incentives that can be insured with repeat health behavior outperforms direct cash payments of the same expected value. Individuals were 70% more likely to return to a health screening when insuring against losing a baseline incentive than they were when paid cash ($p < 0.01$).⁴ In addition, in a recent study we showed that disadvantaged patients at a federally-qualified health center were more likely to repeat a health behavior twice each week over 12 weeks when repetition was insuring against losing a weekly incentive than if they were paid equivalently in cash (see Figure 1; $p < 0.05$).⁵

4.4 END-OF-STUDY DEFINITION

A participant is considered to have completed the study if he or she has completed the baseline assessment, participated in antibody testing and the 6-month follow-up assessment. Participants will be debriefed at the end of the study.

The end of the study is defined as completion of the 6-month follow-up assessment shown in the Schedule of Activities [(SoA), **Section 1.3**].

5 STUDY POPULATION

Our study population will consist of patients on the registries of AltaMed's 12 Los Angeles County primary care clinics, and we will draw a simple random sample of 1000 patient households without replacement. Patients will be randomly selected by address and confirmed to be patients by medical identification number. All members of

the household, both adults and children over the age of 5, are invited to participate in testing, but at least one parent and one child must participate in order for the household to qualify. Partnering with FQHCs will build trust and also provide us access to reliable contact information. In a pilot study at a FQHC, we were able to recruit over 50 families for antibody testing within just 2 days.

5.1 INCLUSION CRITERIA

We will use simple random sampling within the AltaMed patient registry to identify AltaMed patients (and family members) for study recruitment. Adults and children 5 years of age and older will be invited to participate.

5.2 EXCLUSION CRITERIA

Children under 5 years of age will be excluded from the study.

5.3 LIFESTYLE CONSIDERATIONS

Not applicable

5.4 SCREEN FAILURES

Not applicable

5.5 STRATEGIES FOR RECRUITMENT AND RETENTION

Our study population will consist of patients on the registries of AltaMed's 12 Los Angeles County primary care clinics, and we will draw a simple random sample of 1000 patient households without replacement. Patients will be randomly selected by address and confirmed to be patients by medical identification number. All members of the household, both adults and children over the age of 5, are invited to participate in testing, but at least one parent and one child must participate in order for the household to qualify.

Potential study participants must meet the inclusion criteria prior to enrollment. We will use stratified random sampling within the AltaMed patient registry to identify AltaMed patients (and their family members) for study recruitment. Stratification will be by distance to the testing site: using zipcodes, we identified the median distance of patients empanelled in any Los Angeles County AltaMed clinic to the testing site, and we then identified roughly equal random samples of those living less than this median distance (n=3148) and those living more than this median distance (n=3074). In contacting individuals in this sample, all adults and children 5 years of age and older will be invited to participate in testing; at least one adult and one child from a household must be willing to participate in order to be eligible for testing.

Only one adult member (head of household) will be completing the survey. Minors will not be completing survey questions. Children under 5 years of age will be excluded from the study as Tasso SST devices are not recommended for children under 5.

Study participants will be recruited via phone by a culturally competent, bilingual research coordinator from The Henne Group. Consent for participating in the study will be a two-part process. As part of the initial recruitment call, The Henne Group callers will describe the study and ask adult (head of household) if they would like to participate in a survey about COVID-19 and social determinants of health. Consent to participate

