6.3 MEASURES TO MINIMIZE BIAS: RANDOMIZATION AND BLINDING

Randomization will occur at the beginning of the study using the following steps:

NIH Protocol Template for Behavioral and Social Sciences Research Involving Humans

- We will receive a list of 6,222 names from AltaMed Health Services (3074 in the “far” group and 3148 in the “near” group; “far”/“near” based on further/nearer than the median distance of LA AltaMed patient zip codes from the testing site’s zip code).
 - Using this list, The Henne Group will reach out to these participants asking if they would like to participate in the study and have a child in the household.
 - Each household will be assigned a study ID; each participant will have a Study ID number as well as a medical record number (for patients only) from AltaMed to incorporate into the EHR.
 - A list of eligible participants will be available in our HIPAA compliant version of REDCap with their name, research ID and script option (4 options- 2 for messaging/ 2 for financial incentives)
 - Using the randomization feature in REDCap, we will be able to randomize the scripts that each participant will receive.
- Onsite Clinical research coordinators will be blinded to the participant’s condition.

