9.4 STATISTICAL ANALYSES

9.4.1 GENERAL APPROACH

Aim 1 (Hypotheses 1-5): Data from the baseline survey combined with data on which heads of households attended Time 1 testing will be used to address Aim 1. In particular, we will estimate logistic regressions where the dependent variable will be the binary indicator whether the head of household attended Time 1 testing (yes vs. no). The key independent variables will include: 1) prior COVID-19 testing, 2) which SARS-CoV-2 information sources are most trusted, 3) risk aversion, 4) heads of households or family member diagnosis of a health condition (e.g., diabetes, hypertension) and, 5) race/ethnicity, income, discriminatory incidences, household receipt of Supplemental Nutrition Assistance Program (SNAP) or Supplemental Security Income (SSI) benefits, and citing money as the biggest vaccine barrier.

$$\pi = \beta_0 + \beta_1 x_i + \varepsilon_i \quad [1]$$

$\pi = \ln\left(\frac{p}{1-p_i}\right)$; p_i , is the probability of attending Time 1 testing, by head of household i , and β_1 is each head of household reported social determinant of health. This will allow us to identify significant social and behavioral determinants for heterogeneity of effects (currently hypothesized in Hypotheses 1-5 above).

Aim 2 (Hypotheses 1r-4r): Aim 2 will involve regressing Time 2 retesting (yes vs. no) on the following items for Hypotheses 1r-4r: 1r) risk aversion, essential worker status, access to personal protective equipment, and risky forms of transportation (e.g., personal vehicle, carpool, bus), 2r) income, discriminatory incidences, employment status, whether heads of households personally, or other family members suffer from depression and/or mental health issues, and household receipt of Supplemental Nutrition Assistance Program (SNAP) or Supplemental Security Income (SSI) benefits, 3r) Time 1 seropositivity status and, 4r) the Financial Incentive and Messaging study arms.

$$\pi = \beta_0 + \beta_1 x_i + \beta_2 x_i + \beta_3 x_i + \varepsilon_i \quad [2]$$

For Hypotheses 1r-2r, $\pi = \ln\left(\frac{p}{1-p_i}\right)$, is the probability of Time 2 attendance by head of household i given they attended Time 1 testing; β_1 is the main effect of the head of household reported characteristic, β_2 is the main effect of the Financial Incentive, where the lottery condition is the reference, and β_3 is the interaction between the head of household reported social determinant of health and Financial Incentive.

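### The recruitment list is stratified by distance to the testing site, but no planned model includes distance, so Aim 1 associations with attendance may partly reflect travel and distance as an access barrier goes unestimated

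*Combined protocol and SAP*

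**What the plan says.** **Sampling.** Section 5.5 says that "Stratification will be by distance to the testing site". It splits Los Angeles County AltaMed patients at the median zip-code distance and takes roughly equal random samples, 3,148 near and 3,074 far. Section 6.3 agrees: "We will receive a list of 6,222 names from AltaMed Health Services", with the same two counts.

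Other current text describes a different draw. Section 5.1 says "We will use simple random sampling within the AltaMed patient registry". Section 5 says "we will draw a simple random sample of 1000 patient households without replacement", and the opening of 5.5 repeats it.

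**Where testing takes place.** Patients come from the registries of 12 clinics (section 5). The synopsis names one clinic: "The Commerce clinic site will be a participating site enrolling participants". Sections 5.5 and 6.3 measure distance to a testing site in the singular, and 10.1.7 describes monitoring at one clinic. The reference to all sites in 10.1.8 is generic and names no second location.

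**Analysis.** In 9.4.1, Model 1 is a logistic regression of the head of household's attendance at Time 1 testing. The slope "is each head of household reported social determinant of health". The listed predictors include race/ethnicity, income, discriminatory incidents and SNAP/SSI receipt, but not distance. Models 2, 3, 4a and 4b and the secondary analyses in 9.4.2 also lack it. The nearest item is mode of transport, which appears only under Hypothesis 1r as an exposure-risk item.

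**Hypothesis 5 (9.1)** expects minorities and lower socio-economic strata to agree to testing less often, because of fear of discrimination, mistrust, poor past experience and low perceived risk. It does not mention travel.

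**The concern.** Hypothesis 5 is about agreeing to a test, whereas Model 1 measures turning up at a fixed place. Travel can come between the two. If a determinant is related to distance, and distance to attendance, its coefficient in a model without distance mixes the two. A difference produced by travel could then be read as support for mistrust or fear of discrimination. If the disadvantaged group happens to live nearer, a real difference of the Hypothesis 5 kind could be masked. The policy responses differ: more or closer sites in one case, trust-building in the other.

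The synopsis also promises to characterise barriers to access. Distance is the one access variable built into the sampling, and no estimate of its effect is planned.

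**Working it through.** **1. The plan's own figure.** 3,148 + 3,074 = 6,222, which matches section 6.3. The shares are 3,148/6,222 = 50.6% near and 3,074/6,222 = 49.4% far. With a split at the median, this is close to proportional sampling, so the stratification itself distorts almost nothing.

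**2. Where distance is used.**
- Model 1: head-reported determinants only.
- Model 2: determinant, incentive and their interaction.
- Model 3: Time 1 serostatus and a household random intercept.
- Models 4a and 4b: time, factors or arms, interactions with time, and a household random intercept.
- Section 9.4.2: Model 2 again, and seroprevalence on time.
- Section 9.4.6 names sex/gender and race/ethnicity; 9.4.8 is marked not applicable.

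Distance is in none of them.

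**3. How large the effect could be.** The documents give no attendance by distance and no distribution of any determinant by distance, so the following are assumptions:
- odds ratio of attendance, far v near (OR_far): 1.0 to 0.5;
- gap in the share living far between the disadvantaged and the comparison group: 0 to 30 percentage points, centred on 49.4%;
- near attendance: 30% to 70%;
- no effect of the determinant once distance is fixed.

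For a group with far share f, attendance is P(f) = f × p_far + (1 − f) × p_near, where p_far has odds OR_far × p_near/(1 − p_near). The odds ratio of the two groups' P(f) is what a model without distance would show.

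Worked case: p_near = 0.50 and OR_far = 0.5, so p_far = 0.333. A 30-point gap gives f = 0.644 and 0.344.
- Disadvantaged group: 0.644 × 0.333 + 0.356 × 0.50 = 0.393.
- Comparison group: 0.344 × 0.333 + 0.656 × 0.50 = 0.443.
- Difference −5.0 points; odds ratio (0.393/0.607)/(0.443/0.557) = 0.81.

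Spurious odds ratio at 50% near attendance, with the difference in percentage points:

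| OR_far | gap 10 | gap 20 | gap 30 |
|---|---|---|---|
| 0.8 | 0.978 (−0.6) | 0.956 (−1.1) | 0.935 (−1.7) |
| 0.67 | 0.961 (−1.0) | 0.923 (−2.0) | 0.887 (−3.0) |
| 0.5 | 0.934 (−1.7) | 0.872 (−3.3) | 0.814 (−5.0) |

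The odds ratios hardly change at 30% or 70% near attendance. They are exactly 1.00 if OR_far = 1 or the gap is zero.

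**4. Direction.** Exchanging the two groups inverts each ratio, so 0.814 becomes 1/0.814 = 1.23. A simpler example takes near and far groups of equal size and attendance of 50% near and 30% far.
- Group shares 40% near and 60% far: 0.4 × 50% + 0.6 × 30% = 38% attendance, against 42% in the comparison group. Odds ratio (0.38/0.62)/(0.42/0.58) = 0.85.
- Shares reversed: 42% v 38%, odds ratio 1.18.

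**The case against.** A reader might infer that the Aim 1 effects are confounded with travel. The documents do not support that. Confounding needs distance to be related both to attendance and to the determinant, and they report neither. Nor do they say which group lives farther away. Only the weaker statement, that the associations may partly reflect travel, can be made.

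A reader might also infer that leaving out a stratification factor is what creates the problem. It is not. The sampling is nearly proportional, and the same question would arise under a simple random sample. Section 6.3 does not describe randomisation as stratified by distance, so the convention of adjusting for randomisation strata does not apply. The stratification shows only that the planners thought distance relevant and that it is known at sampling.

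The strongest objection is that distance may lie on the path from low income or minority status to non-attendance. The unadjusted coefficient is then a legitimate total association, and adjustment changes the question rather than removing a bias. Section 9.4.1 says Model 1 is meant to identify significant determinants, which fits that reading. This stands, and it is why both versions should be reported. Hypothesis 5 nevertheless names non-travel mechanisms, and the unadjusted version alone cannot separate them from travel.

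Two smaller points have some force. The predictor list in 9.4.1 is introduced as what the key variables will include, so it is not strictly closed. Sections 5.5 and 7.1 also collect reasons from people who decline testing, through which distance could surface. That does not cover people who accept an appointment and fail to come, and it gives no estimate of a distance effect.

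**Conclusion.** The point holds in a limited form. The list is stratified by distance to the one testing site described, no planned analysis uses distance, and the Aim 1 outcome is attendance in person. The race/ethnicity, income and SNAP/SSI associations may therefore partly reflect travel, and the access barrier is left unestimated.

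Over the assumed ranges the spurious odds ratio runs from 1.00 to about 0.8 (0 to −5 percentage points), or up to about 1.2 if the disadvantaged group lives nearer. These figures rest wholly on the assumptions in the working and are not predictions for this trial. They also take the near/far mix of analysed heads of household to be that of the list.

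A reader might extend the point to the trial's main comparison. It does not reach that far: the Hypothesis 4r contrasts are between randomised arms and are not confounded by distance in expectation. What is at stake is how Aim 1 is interpreted.

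The two descriptions of the sampling are a separate inconsistency in current text and need reconciling in any case.

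**What to change.** - **Data.** State that the near/far label on the recruitment list is carried into the analysis file. Section 6.3 lists name, research ID and script option as the REDCap fields, so this needs to be explicit. The label is the safer choice over zip-code distance, because 10.1.3 says the research team will not have identifying information.
- **Model 1 (9.4.1).** Add the near/far term, report its coefficient as an access barrier, and show the determinant effects with and without it. Say which version addresses Hypothesis 5 and which describes the total association. State also whether the determinants are fitted jointly or one at a time, since the model is written with a single slope.
- **Models 2 and 3.** Including the term is optional, on the same grounds, for the non-randomised terms (determinant main effects, Time 1 serostatus).
- **Models 4a and 4b.** Inclusion serves precision only.
- **Sampling text.** Reconcile sections 5, 5.1 and the opening of 5.5 (simple random sampling; 1,000 households in 5 and 5.5) with the stratified list of 6,222 names in 5.5 and 6.3.

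The cost is SAP wording, one field transferred from the list, one degree of freedom per model and one extra reported version of Model 1. A two-level label captures travel only coarsely, so some travel effect within each stratum would remain.
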